  - **Immune-related meningoencephalitis (all grades):**

- Permanently discontinue pembrolizumab.
- Refer patient to a neurologist.
- Initiate treatment with corticosteroids equivalent to 1-2 mg/kg/day IV methylprednisolone and convert to 1-2 mg/kg/day oral prednisone or equivalent upon improvement.
- If the event does not improve within 48 hours after initiating corticosteroids, consider adding an immunosuppressive agent.
- If event resolves to Grade 1 or better, taper corticosteroids over no less than 4 weeks.

- **Myositis**

Myositis or inflammatory myopathies are a group of disorders sharing the common feature of inflammatory muscle injury; dermatomyositis and polymyositis are among the most common disorders. Initial diagnosis is based on clinical (muscle weakness, muscle pain, skin rash in dermatomyositis), biochemical (serum creatine kinase increase), and imaging (electromyography/MRI) features, and is confirmed with a muscle biopsy.

- For **Grade 1** events: Continue pembrolizumab, refer patient to a rheumatologist or neurologist, and initiate treatment as per institutional guidelines.
- For **Grade 2** events:
  - Withhold pembrolizumab for up to 12 weeks after event onset. Pembrolizumab may be withheld for a longer period of time (i.e. >12 weeks after event onset) to allow for corticosteroids (if initiated) to be reduced to the equivalent of 10 mg/day or less of oral prednisone.
  - Refer patient to a rheumatologist or neurologist.
  - Initiate treatment as per institutional guidelines.
  - Consider treatment with corticosteroids equivalent to 1-2 mg/kg/day IV methylprednisolone and convert to 1-2 mg/kg/day oral prednisone or equivalent upon improvement.
  - If corticosteroids are initiated and the event does not improve within 48 hours after initiating corticosteroids, consider adding an immunosuppressive agent.
  - If event resolves to Grade 1 or better and patient is stable on replacement therapy, resume pembrolizumab. If corticosteroids have been initiated, they must be tapered over no less than 4 weeks to the equivalent of 10 mg/day oral prednisone or less before pembrolizumab may be resumed.
- For **Grade 3** events:
  - Withhold pembrolizumab for up to 12 weeks after event onset.

Pembrolizumab may be withheld for a longer period of time (i.e. >12 weeks after event onset) to allow for corticosteroids (if initiated) to be reduced to the equivalent of 10 mg/day or less of oral prednisone.

- Refer patient to a rheumatologist or neurologist.
- Initiate treatment as per institutional guidelines. Respiratory support may be required in more severe cases.
- Initiate treatment with corticosteroids equivalent to 1-2 mg/kg/day IV methylprednisolone, or higher-dose bolus if patient is severely compromised (e.g., cardiac or respiratory symptoms, dysphagia, or weakness that severely limits mobility); convert to 1-2 mg/kg/day oral prednisone or equivalent upon improvement.
- If event does not improve within 48 hours after initiating corticosteroids, consider adding an immunosuppressive agent.
- If event resolves to Grade 1 or better and patient is stable on replacement therapy, resume pembrolizumab. If corticosteroids have been initiated, they must be tapered over no less than 4 weeks to the equivalent of 10 mg/day oral prednisone or less before pembrolizumab may be resumed.
- For recurrent events, treat as a Grade 4 event.

○ For **Grade 4** events:

- Permanently discontinue pembrolizumab.
- Refer patient to a rheumatologist or neurologist.
- Initiate treatment as per institutional guidelines. Respiratory support may be required in more severe cases.
- Initiate treatment with corticosteroids equivalent to 1-2 mg/kg/day IV methylprednisolone, or higher-dose bolus if patient is severely compromised (e.g., cardiac or respiratory symptoms, dysphagia, or weakness that severely limits mobility); convert to 1-2 mg/kg/day oral prednisone or equivalent upon improvement.
- If the event does not improve within 48 hours after initiating corticosteroids, consider adding an immunosuppressive agent.
- If event resolves to Grade 1 or better, taper corticosteroids over no less than 4 weeks.

- **Infusion-related reactions**

Signs and symptoms usually develop during or shortly after drug infusion and generally resolve completely within 24 hours of completion of infusion. No premedication is indicated for the administration of Cycle 1 of pembrolizumab. However, patients who experience an IRR with Cycle 1 of pembrolizumab may receive premedication with antihistamines or antipyretics/analgesics (e.g., acetaminophen) for subsequent infusions.

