### **MANAGEMENT GUIDELINES**

#### **▪ Immune-related hepatitis**

Immune-related hepatitis has been associated with the administration of pembrolizumab. Patients with right upper quadrant pain and/or unexplained nausea or vomiting should have liver function tests (LFTs) performed immediately and reviewed before administration of the next dose of study drug.

For patients with elevated LFTs, concurrent medication, viral hepatitis, biliary obstruction, and toxic or neoplastic etiologies should be considered and addressed, as appropriate.

- For **Grade 1 events**, continue pembrolizumab and monitor LFTs until values resolve to within normal limits or to baseline values.
- For **Grade 2 events of >5 days' duration**:
  - Withhold pembrolizumab for up to 12 weeks after event onset. Pembrolizumab may be withheld for a longer period of time (i.e. >12 weeks after event onset) to allow for corticosteroids (if initiated) to be reduced to the equivalent of 10 mg/day or less of oral prednisone. The acceptable length of the extended period of time will be determined by the investigator.
  - Initiate treatment with systemic corticosteroids equivalent to 1-2 mg/kg/day oral prednisone.
  - Monitor liver function tests more frequently until returned to baseline values (consider weekly).
  - If event resolves to Grade 1 or less, resume pembrolizumab. If corticosteroids have been initiated, they must be tapered over no less than 4 weeks to the equivalent of 10 mg/day oral prednisone or less before pembrolizumab may be resumed.
- For **Grade 3-4 events**:
  - Permanently discontinue pembrolizumab.
  - Consider referral to gastrointestinal specialist for evaluation and liver biopsy to establish etiology of hepatic injury.
  - Initiate treatment with systemic corticosteroids equivalent to 1-2 mg/kg/day oral prednisone.
  - If the event does not improve within 48 hours after initiating corticosteroids, consider adding an immunosuppressive agent.
  - If event resolves to Grade 1 or better, taper corticosteroids over no less than 4 weeks.

- **Immune-related pneumonitis**

Dyspnea, cough, fatigue, hypoxia, pneumonitis, and pulmonary infiltrates have been associated with the administration of pembrolizumab. Patients will be assessed for pulmonary signs and symptoms throughout the study and will have computed tomography (CT) scans of the chest performed at every tumor assessment.

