All pulmonary events should be thoroughly evaluated for other commonly reported etiologies such as pneumonia or other infection, lymphangitic carcinomatosis,

pulmonary embolism, heart failure, chronic obstructive pulmonary disease, or pulmonary hypertension.

Management guidelines for pulmonary events, including pneumonitis:

- For **Grade 1 events**, continue pembrolizumab and monitor closely. Re-evaluate on serial imaging and consider referral to a pulmonary specialist.
- For **Grade 2 events**:
  - Withhold pembrolizumab for up to 12 weeks after event onset. Pembrolizumab may be withheld for a longer period of time (i.e. >12 weeks after event onset) to allow for corticosteroids (if initiated) to be reduced to the equivalent of 10 mg/day or less of oral prednisone.
  - Initiate treatment with systemic corticosteroids equivalent to 1-2 mg/kg/day oral prednisone.
  - Refer patient to pulmonary specialist and consider bronchoscopic alveolar lavage.
  - When symptoms improve to Grade 1 or less, resume pembrolizumab. Steroid taper should be started and continued over no less than 4 weeks.
- For **Grade 3-4 events**:
  - Permanently discontinue pembrolizumab.
  - Initiate treatment with corticosteroids equivalent to 1-2 mg/kg/day oral prednisone.
  - If the event does not improve within 48 hours after initiating corticosteroids, consider adding an immunosuppressive agent.
  - If event resolves to Grade 1 or better, taper corticosteroids over no less than 4 weeks.
- Add prophylactic antibiotics for opportunistic infections in the case of prolonged steroid administration.
- **Immune-related colitis**  
Subjects should be carefully monitored for signs and symptoms of enterocolitis (such as diarrhea, abdominal pain, blood or mucus in stools, with or without fever) and of bowel perforation (such as peritoneal signs and ileus).

All events of diarrhea or colitis should be thoroughly evaluated for other more common etiologies. For events of significant duration or magnitude or associated with signs of systemic inflammation or acute-phase reactants (e.g. increased C-reactive protein, platelet count, or bandemia): Perform sigmoidoscopy (or colonoscopy, if appropriate) with colonic biopsy, with three to five specimens for standard paraffin block to check

for inflammation and lymphocytic infiltrates to confirm colitis diagnosis.

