**Table 5 Dose Modification Guidelines for Pembrolizumab-Related Adverse Events**

Toxicity	Hold Treatment For Grade	Timing for Restarting Treatment	Treatment Discontinuation
Diarrhea/Colitis	2-3	Toxicity resolves to Grade 0-1	Toxicity does not resolve within 12 weeks of last dose or inability to reduce corticosteroid to 10 mg or less of prednisone or equivalent per day within 12 weeks
	4	Permanently discontinue	Permanently discontinue
	2	Toxicity resolves to Grade 0-1	Toxicity does not resolve within 12 weeks of last dose
AST, ALT, or Increased Bilirubin	3-4	Permanently discontinue (see exception below) a	Permanently discontinue
Toxicity	Hold Treatment For Grade	Timing for Restarting Treatment	Treatment Discontinuation
Type 1 diabetes mellitus (if new onset) or Hyperglycemia	T1DM or 3-4	Hold pembrolizumab for new onset Type 1 diabetes mellitus or Grade 3-4 hyperglycemia associated with evidence of beta cell failure	Resume pembrolizumab when patients are clinically and metabolically stable
Hypophysitis	2-4	Toxicity resolves to Grade 0-1. Therapy with pembrolizumab can be continued while endocrine replacement therapy is instituted	Toxicity does not resolve within 12 weeks of last dose or inability to reduce corticosteroid to 10 mg or less of prednisone or equivalent per day within 12 weeks
Hyperthyroidism	3	Toxicity resolves to Grade 0-1	Toxicity does not resolve within 12 weeks of last dose or inability to reduce corticosteroid to 10 mg or less of prednisone or equivalent per day within 12 weeks
	4	Permanently discontinue	Permanently discontinue
Hypothyroidism		Therapy with pembrolizumab can be continued while thyroid replacement therapy is instituted	Therapy with pembrolizumab can be continued while thyroid replacement therapy is instituted
Infusion Reaction	2 b	Toxicity resolves to Grade 0-1	Permanently discontinue if toxicity develops despite adequate premedication
	3-4	Permanently discontinue	Permanently discontinue
Pneumonitis c	2	Toxicity resolves to Grade 0-1	Toxicity does not resolve within 12 weeks of last dose or inability to reduce corticosteroid to 10 mg or less of prednisone or equivalent per day within 12 weeks
	3-4	Permanently discontinue	Permanently discontinue
Renal Failure or Nephritis	2	Toxicity resolves to Grade 0-1	Toxicity does not resolve within 12 weeks of last dose or inability to reduce corticosteroid to 10 mg or less of prednisone or equivalent per day within 12 weeks

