**Note: Permanently discontinue for any severe or Grade 3 drug-related AE that recurs or any life-threatening event.**

a For patients with liver metastasis who begin treatment with Grade 2 AST or ALT, if AST or ALT increases by greater than or equal to 50% relative to baseline and lasts for at least 1 week then patients should be discontinued.

b If symptoms resolve within one hour of stopping drug infusion, the infusion may be restarted at 50% of the original infusion rate (e.g., from 100 mL/hr to 50 mL/hr). Otherwise dosing will be held until symptoms resolve and the subject should be premedicated for the next scheduled dose; Refer to Table 4—Infusion Treatment Guidelines for further management details.

c For grade 2 pneumonitis, should this recur, pembrolizumab should be discontinued.

d Patients with intolerable or persistent Grade 2 drug-related AE may hold study medication at physician discretion. Permanently discontinue study drug for persistent Grade 2 adverse reactions for which treatment with study drug has been held, that do not recover to Grade 0-1 within 12 weeks of the last dose.

Dosing interruptions are permitted in the case of medical / surgical events or logistical reasons not related to study therapy (e.g., elective surgery, unrelated medical events, patient vacation, and/or holidays). Subjects should be placed back on study therapy within 3 weeks of the scheduled interruption, unless otherwise discussed with the Sponsor. The reason for interruption should be documented in the patient's study record.

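### Section 8.2.8: Grade 2 pneumonitis is the only one of 15 twelve-week holds that lets pembrolizumab resume with no steroid dose to be reached first

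*Combined protocol and SAP*

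**What the plan says.** Section 8.2.8 (Supportive Care Guidelines) sets out management by toxicity and grade. The Grade 2 pneumonitis block has three relevant steps.

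- **Hold.** "Withhold pembrolizumab for up to 12 weeks after event onset". The hold may run longer "to allow for corticosteroids (if initiated) to be reduced to the equivalent of 10 mg/day or less of oral prednisone".
- **Steroid.** "Initiate treatment with systemic corticosteroids equivalent to 1-2 mg/kg/day oral prednisone". This is unconditional.
- **Restart.** "When symptoms improve to Grade 1 or less, resume pembrolizumab. Steroid taper should be started and continued over no less than 4 weeks".

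The Grade 2 hepatitis block uses the same hold and the same steroid-start sentence. Its restart step differs: if corticosteroids were started, "they must be tapered over no less than 4 weeks to the equivalent of 10 mg/day oral prednisone or less before pembrolizumab may be resumed".

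In Section 9.1, the Table 5 row for Grade 2 pneumonitis allows restart once the toxicity is Grade 0-1. It calls for discontinuation if the toxicity does not resolve within 12 weeks of the last dose, or on "inability to reduce corticosteroid to 10 mg or less of prednisone or equivalent per day within 12 weeks". Footnote c adds: "For grade 2 pneumonitis, should this recur, pembrolizumab should be discontinued".

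**The concern.** The pneumonitis restart step depends on symptom grade alone. It mentions a taper, but gives no dose to reach before the next infusion and does not say whether the taper begins before, with or after resumption. An investigator who follows it literally could give the PD-1 inhibitor while the subject is still well above 10 mg/day of prednisone. The protocol rules that out in every other block with a twelve-week hold.

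This matters for the subject because Grade 2 pneumonitis that recurs after restart ends pembrolizumab treatment. The protocol gives no reason for a looser rule in the lung than in the liver, bowel or kidney, so the difference reads as an omission.

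**Working it through.** The plan states no figure on this point. The check is a count of blocks, a comparison of wording, and one illustrative dose calculation.

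**1. Count.** Every block in Section 8.2.8 with the twelve-week hold was listed by how it starts steroids, and its restart step was checked for the condition of 10 mg/day or less before resumption.

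| Steroid start | Blocks | Number | With the condition |
|---|---|---|---|
| Always 1-2 mg/kg/day | hepatitis G2, **pneumonitis G2**, colitis G3, hypophysitis G2-3, adrenal insufficiency G2-4, nephritis G2, pancreatitis G2-3, myositis G3 | 8 | 7 |
| Always 10 mg/day at first | dermatologic G3 | 1 | 1 |
| Conditional, or only to be considered | colitis G2, amylase/lipase G3-4, myocarditis G2, myositis G2 | 4 | 4 |
| Topical drops named | ocular G2 | 1 | 1 |
| Institutional guidelines | neuropathy G2 | 1 | 1 |
| **Total** | | **15** | **14** |

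The one block without the condition is Grade 2 pneumonitis. The type 1 diabetes and symptomatic thyroid holds also name no steroid dose. They are not twelve-week holds and start no corticosteroid, so they are not counted.

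**2. Does other text supply the condition?**

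- The hold bullet in the pneumonitis block names 10 mg/day, but only as a reason why the hold may be extended. The other 14 blocks contain the same hold wording and still add the explicit restart condition.
- Table 5 names 10 mg/day for Grade 2 pneumonitis only in its discontinuation column. Its restart column names no steroid dose for any toxicity.
- Section 8.2.6 restricts systemic glucocorticoids during treatment but exempts their use for immune-related events of clinical interest, so it does not block re-dosing on steroids given for pneumonitis.

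**3. Dose at re-dosing (illustration).** Assumptions, none of them from the documents: body weight 70 kg, and a straight-line 28-day taper to 10 mg/day begun on the day Grade 1 is reached. The 1-2 mg/kg/day, the four-week minimum taper, the 10 mg/day threshold and the three-week dosing interval are the protocol's.

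- Starting dose: D0 = 70 × 1 = 70 mg/day to 70 × 2 = 140 mg/day.
- Dose on taper day t: D(t) = D0 − (D0 − 10) × t/28.
- Infusion on day 0: 70 to 140 mg/day.
- Infusion on day 21: 70 − 60 × 21/28 = 25 mg/day, to 140 − 130 × 21/28 = 42.5 mg/day.

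**4. Added wait under the usual condition.** If Grade 1 is reached s days into that taper, the extra wait is 28 − s days: 28 days at s = 0 and none at s = 28. It exceeds 28 days if the taper is slower or starts later. The range is therefore 0 to 28 days or more, and the text does not narrow it.

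**The case against.** The best case against acting has four parts.

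- **The text is advisory.** Section 8.2.8 introduces its measures as suggestions, while the binding rule is Table 5, and the pneumonitis block agrees with the Table 5 restart column. This is true, but the other 14 blocks sit under the same introduction and still state the condition as mandatory. Agreement with Table 5 shows only that Table 5 does not close the gap.
- **The threshold can be inferred.** Extending the hold so that steroids can fall to 10 mg/day makes little sense unless 10 mg/day governs restart, and the block also refers the subject to a pulmonary specialist. Both points make re-dosing at high steroid doses less likely in practice. Neither makes it contrary to the text.
- **The harm is not quantified.** The documents do not link re-dosing above 10 mg/day to recurrence and give no Grade 2 pneumonitis rate. Few subjects would be affected among 31 evaluable (at most 37 enrolled), and the illustrative doses rest on assumptions. All of this stands and limits the weight of the point.
- **Table 5 has its own tension.** The block allows a hold beyond 12 weeks for the taper, while Table 5 discontinues if 10 mg/day is not reached within 12 weeks. This is a fair observation, but a separate one. The proposed edit neither causes nor resolves it.

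**Conclusion.** The concern holds. Fourteen of 15 twelve-week hold blocks require steroids, if started, to be at 10 mg/day or less before pembrolizumab resumes. Grade 2 pneumonitis does not, although it always starts 1-2 mg/kg/day. The count and the wording come directly from the text and need no assumption. The mg/day figures and the length of the added wait depend on the assumed weight and taper, and show only what the wording permits.

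This is an inconsistency in safety guidance that should be corrected. It has no bearing on sample size or power, and no effect on progression-free survival is claimed.

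**What to change.** In the Grade 2 pneumonitis block of Section 8.2.8, keep restart at Grade 1 or less and replace the sentence on the steroid taper with the clause from the Grade 2 hepatitis block: if corticosteroids were started, "they must be tapered over no less than 4 weeks to the equivalent of 10 mg/day oral prednisone or less before pembrolizumab may be resumed". The clinical lead should sign this off. If the looser rule is intended, the protocol should say so and state the order of taper and re-dosing.

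The cost is one sentence, bundled with the next amendment. Sample size and visits are unaffected. Table 5 can stay as it is for this purpose, since its restart column is already silent on steroid dose for the other toxicities. The one downside is that pembrolizumab may restart later in the few subjects with Grade 2 pneumonitis, a delay the protocol already accepts in the other 14 blocks.

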**Table 4 Infusion Reaction Treatment Guidelines**

NCI CTCAE Grade	Treatment	Premedication at subsequent dosing
Grade 1 Mild reaction; infusion interruption not indicated; intervention not indicated	Increase monitoring of vital signs as medically indicated until the subject is deemed medically stable in the opinion of the investigator.	None
Grade 2 Requires infusion interruption but responds promptly to symptomatic treatment (e.g., antihistamines, NSAIDS, narcotics, IV fluids); prophylactic medications indicated for <=24 hrs	
Stop Infusion and monitor symptoms. Additional appropriate medical therapy may include but is not limited to:
 
 
IV fluids
 
Antihistamines
 
NSAIDS
 
Acetaminophen
 
Narcotics
 
 
Increase monitoring of vital signs as medically indicated until the subject is deemed medically stable in the opinion of the investigator.
 
If symptoms resolve within one hour of stopping drug infusion, the infusion may be restarted at 50% of the original infusion rate (e.g., from 100 mL/hr to 50 mL/hr). Otherwise dosing will be held until symptoms resolve and the subject should be premedicated for the next scheduled dose.
 
Subjects who develop Grade 2 toxicity despite adequate premedication should be permanently discontinued from further trial treatment administration.
	
Subject may be premedicated 1.5h (<math>\pm</math> 30 minutes) prior to infusion of pembrolizumab (MK-3475) with:
 
Diphenhydramine 50 mg po (or equivalent dose of antihistamine).
 
Acetaminophen 500-1000 mg po (or equivalent dose of antipyretic).

Grades 3 or 4 Grade 3: Prolonged (i.e., not rapidly responsive to symptomatic medication and/or brief interruption of infusion); recurrence of symptoms following initial improvement; hospitalization indicated for other clinical sequelae (e.g., renal impairment, pulmonary infiltrates) Grade 4: Life-threatening; pressor or ventilatory support indicated	
Stop Infusion. Additional appropriate medical therapy may include but is not limited to:
 
 
IV fluids
 
Antihistamines
 
NSAIDS
 
Acetaminophen
 
Narcotics
 
Oxygen
 
Pressors
 
Corticosteroids
 
Epinephrine
 
 
Increase monitoring of vital signs as medically indicated until the subject is deemed medically stable in the opinion of the investigator.
 
Hospitalization may be indicated.
 
Subject is permanently discontinued from further trial treatment administration.
	No subsequent dosing
Appropriate resuscitation equipment should be available in the room and a physician readily available during the period of drug administration.		

#### 8.4. Azacitidine

Azacitidine is supplied as a lyophilized powder in a single-dose vial. Each vial contains 100 mg of azacitidine. Azacitidine is administered at a dose of 50 mg/m^2 by SubQ injection, in rotating sites (thigh, abdomen, or upper arm) repeated for 5 consecutive business days. This cycle should be repeated after 4 weeks. Patients should be premedicated with standard anti-emetic therapy.

Contraindications to the administration of azacitidine include advanced malignant hepatic tumors and hypersensitivity to azacitidine or mannitol. Patients with severe preexisting hepatic

impairment are at higher risk for toxicity. Azacitidine is primarily excreted by the kidneys. No formal drug interaction studies with azacitidine have been conducted. Whether azacitidine metabolism may be affected by known microsomal enzyme inhibitors or inducers in the liver has not yet been studied. *In vitro* studies have shown that azacitidine does not cause inhibition of CYP2B6 and CYP2C8 but the potential of azacitidine to inhibit other cytochrome P450 enzymes is not known. Other *in vitro* studies indicate that azacitidine does not induce CYP 1A2, 2C19, or 3A4/5.

